The objectives of this study are to assess cost-effectiveness of a Young Moms Program that incorporates a traditional Parents as Teachers home visiting parenting program to that of a hybrid virtual/home based Parents as Teachers program, against short-term outcomes, which in turn will serve as leading indicators of longer-term results. Specific outcomes are outlined in the measures section.

Methods and Measures

This is a community-engaged research collaboration between the non-profit Imprints Cares, the WFBMC Birth Center, and WFSOM. Because YMP is a tiered program model, services meet parents where they are through a “warm hand-off” approach that uses on one-on-one consultation and assessment-based interventions. The YMP is designed to address systemic barriers to the health and stability of young moms and their children such as the lack of coordination of service delivery or logistical barriers within the health system. The YMP also streamlines the referral pipeline, connecting

Protocol version:

Template updated 9.24.14

moms to evidence-based resources, and ensuring children complete all recommended assessments prior to kindergarten.

This research project is a pilot randomized controlled trial. We expect a total of 30 participants, 15 in each arm of the study. For inclusion into this study participants must be an immediately post-partum mother, between 14-21 years of age who will reside with her newborn. The mother must be referred from either the Birth Center at Wake Forest Baptist Health or from one of the Wake Forest Baptist Health PPC partner practices. Exclusion criteria include that newborn of participating mothers must be ≥ 35 weeks of gestation and not have an extended NICU stay. These populations are excluded because medically complex newborns and a prolonged separation during the intervention period will directly affect our outcome measures. Participants must speak English or Spanish given our parent educators and other group participants are limited to those languages. Males are excluded as participants, the intervention and many of the outcome measures are only applicable to female participants.

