Participants will be randomly assigned to one of the two variants of the Parents as Teacher home visitation model, traditional or hybrid. The study's research coordinator, who is not directly involved with the delivery of services, will manage the randomization and assignment process; all consented participants will be given a system-generated unique identifier, which cannot be linked to patient identity by anyone except the research coordinator. This information will be securely maintained by the research coordinator. The team will complement the treatment groups' data with population data extracted from WFBMC's Epic system. Analysts will use rigorous techniques (e.g, Propensity Score Matching) to create a matched control group.

Both formats and all interventions included in the study are the current models of care for our existing PAT/YMP services. The hybrid model was developed in 2020 in response to the need to move services virtually as home visitation was not allowed during COVID-19 lockdown.

Through the traditional PAT model, participants will be referred through a warm hand-off from the Birth Center or one of WFBH community pediatric centers to Imprints Cares. A PAT certified family educator will meet with the family focusing on a one-on-one consultation and assessment-based interventions. Participants in the traditional PAT model will receive two home visits a month and participate in monthly peer (group) connections throughout the study period.

In the hybrid PAT model, participants will be referred through a warm hand-off to Imprints Cares from the Birth Center or one of WFBH community pediatric centers. A PAT certified family educator will meet with the family focusing on a one-on-one consultation and assessment-based interventions. Study participants will begin receiving services by participating in the virtual "What You Do Matters" program, an evidence-based PAT curriculum. After completion of the virtual program, young moms will begin receiving once a month home visits and participate in monthly peer (group) connections.

Protocol version:

Template updated 9.24.14

By including two variants in this pilot project, the study team will assess the cost-effectiveness of the two approaches, against short-term outcomes, which in turn will serve as leading indicators of longer-term results. At the end of the official study period, participants will be eligible to continue in the program until the child's school entry into kindergarten.

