Both models will be staffed by qualified family educators that have been trained in the Parents as Teachers Foundational Curriculum, the Circle of Security model, and breastfeeding educator certification program. Imprints Cares also has a mental/behavioral health family educator on staff to address emergent mental/behavioral concerns as they arise. These approaches have been documented to nurture parental attachment and secure relationships^{xi}.

Outcome Measures

The team will use several published assessments:

Protective Factors Survey. The Protective Factors Survey (PFS) is a validated parent survey designed that assesses protective factors in five areas: family functioning/resiliency, social support, concrete support, nurturing and attachment, and knowledge of parenting/child development. The PFS will be implemented at week one, week six, and end of study, as it requires parent-child interactions for completion.

Ages and Stages Questionnaire 3rd edition. The Ages and Stages Questionnaire (ASQ 3) is a validated developmental screening designed for use by and with parents. The ASQ 3 screens for developmental milestones in communication, gross motor, fine motor, problem solving, and personal-social skills. The ASQ 3 will be implemented at the recommended intervals designed by its publisher (2, 4, and 6 months).

Ages and Stages Questionnaire: Social-Emotional 2nd edition. Similar to the ASQ 3, the Ages and Stages Questionnaire: Social-Emotional (ASQ:SE 2) is a validated screening of social and emotional behaviors. The ASQ:SE 2 will be implemented at the recommended intervals designed by its publisher (2, 4, and 6 months).

Patient Health Questionnaire. The Patient Health Questionnaire (PHQ 9) is a self-administered questionnaire that is validated for use in assessing the severity of depression. The PHQ 9 will be administered as a baseline assessment as well as an end-of-study assessment.

StimQ2-I. The StimQ2-I is a validated, interview-based assessment of home environments for use with infants ages five to 12 months. The StimQ2-I focuses on cognitive stimulation by the primary caregiver and contains several scales: Availability of Learning Materials, Reading-Verbal, Parental Involvement in Developmental Advance, and Parental Verbal Responsivity. The StimQ2-I will be implemented at the end of study, as it requires parent-child interactions for completion.

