In addition to these assessments, the team will use an intake questionnaire to capture parent demographic and health information as well as baseline knowledge about child development and parenting and a monthly questionnaire used to assess mother's status on continuance of secondary education, breastfeeding, and use of contraception. A monthly questionnaire, which will be developed for use in this study, also will assess infant developmental milestones.

Further, the team will access health information captured in WFBMC's Epic system, including completion of Well-Child Visits and recommended immunizations. A WFBMC study team member will extract data on participants as well as a matched control group. The study team will conclude the study with participant focus groups, to collect additional qualitative feedback and insights. Finally, the team will develop and implement Fidelity of Implementation (FOI) quality

Protocol version:

Template updated 9.24.14

assurance guidelines and checklists to capture the degree to which project services are delivered as expected. FOI scores will be used as a predictive variable with the goal of establishing a minimum service threshold for short-term outcomes.

Proposed Statistical Analyses

Descriptive Analyses. All data will be subject to descriptive analyses, including measures of central tendencies and frequency distributions, as appropriate for the type of data collected. Descriptive analyses will support our understanding of participant characteristics and equivalency of samples in the traditional and hybrid models.

Inferential Analyses. Inferential analyses, such as t-tests, multiple regression, and Analysis of Variance, will be conducted to test for change between baseline and end-of-study data collections with the PHQ 9, and the PFS. The PFS will be administered at service week one, service week six, and at the end-of-study to assess differences between the models at promoting protective and nurturing behaviors. Tests also will be used to assess differences between the models on maternal outcomes such as continuance of secondary education, breastfeeding, and use of contraception and child-focused outcomes such as STIMQ2-I, completion of Well Child Visits and immunizations. The study team will work with CTSI Biostatistical Support services to advise and guide the analytic approach.

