Proposed Cost Effectiveness Study Design. One of the primary challenges of completing cost studies is fully accounting for all costs and benefits. Therefore, the study team will use this project period to identify the spectrum of costs associated with serving one young mother and her child. These data will be compiled to generate an average cost of service and establish outliers that exist when there are particularly risky or traumatic cases. In addition, the team will establish short-term benefits (achievable after six-months of services) along with the program implementation conditions necessary to achieve them. We will utilize the services of BERD and Q-Pro to assist in advising in areas of study design, data analysis, and data management.

Study Timeline

Study Milestone	M1	M2	M3	M4	M5	M6	M7	M8	M9	M10	M11	M12
Achieve IRB approval	•											
Enrollment of teen moms		•	•	•								
Baseline data collected		•	•	•								
Services delivered	•	•	•	•	•	•	•	•	•	•		
Week one data collected	•	•	•									
Week six data collected		•	•	•								
ASQ/ASQ-SE data collected (2,4, and 6m)			•	•	•	•	•	•	•	•	•	•
Monthly questionnaires and FOI checklists completed			•	•	•	•	•	•	•	•	•	
End of study data collected											•	•
Analysis and reporting completed												•

The project will track numerous milestones, including:

- Submission of IRB application and receipt of IRB approval. This milestone is critical as the project will not move forward without IRB approval.
- Enrollment of young moms by the project's four month. All participants will need to be enrolled by month four to ensure moms in both models can receive at least six months of home visitation services. In the traditional model, home visitation starts immediately upon

Protocol version:

Template updated 9.24.14

enrollment. In the hybrid model, home visitation starts at the completion of the six-week What You Do Matters virtual class.

- Collection of all baseline data. Baseline data will be collected at the time of enrollment and will consist of the enrollment form and the PHQ 9.
- Collection of week one and week six data. Data will be collected during the participant's first and sixth week (at the close of the What You Do Matters course) of services in both models (PFS).
- Collection of monthly questionnaires. Monthly questionnaires will be implemented with each participant, on a schedule developed by the family educator.

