- Collection of ASQ and ASQ:SE data as recommended by the publisher (2, 4, 6m).
- Collection of end-of-study data (6 months after enrollment). In the final month of services, the team will collect the ASQ, ASQ:SE, PHQ 9, the PFS and the StimQ2-I.
- Collection of FOI checklist data. Project staff and supervisors will complete FOI checklists on a monthly basis. Each model will have its own checklist.
- WFBMC data extraction and compilation of analysis files. One of the WFBMC team members will work to securely extract health data for treatment and matched control group participants from the Epic system.

Human Subjects Protection

Subject Recruitment Methods

No additional PHI will be accessed or printed/transcribed above and beyond what is part of standard patient care and pre-defined job descriptions.

OB Home Visiting Staff

- 1) Our OB Home Visiting Nursing Staff as part of their standard workflow identify and visit all post-partum mothers that reside in Forsyth County, NC.
- 2) Of those, they will identify mothers that meet inclusion criteria for the study (14-21 years old, Spanish or English Speaking, will reside with their newborn upon discharge, and will follow up with a Wake Forest Baptist Health Pediatrician).
- 3) During their standard meeting, while the mother is still inpatient from her delivery, OB home visiting staff per their standard workflow will ask if the mother would like referral to Imprints Cares. If they identify a likely eligible participant, they will introduce study at that time, without promising the patient they are eligible. If the patient is interested in referral for either the study or services not provided as part of the study, the team will make a referral to Imprints Cares. The referral will indicate if the patient appears to be eligible for the study or not.

Imprints Cares

- 1) After referral from the PPC primary care physician or the OB Home Visiting Nursing Staff to the Imprints Cares program, intake staff will assess if new mothers meet criteria for participation in the study (14-21 years old, Spanish or English Speaking, will reside with their newborn upon discharge, and will follow up with a Wake Forest Baptist Health Pediatrician).

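### The cost-effectiveness section undertakes to establish benefits of six months of services, but the design identifies only the difference between two served arms

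*Combined protocol and SAP*

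**What the plan says.** The section Proposed Cost Effectiveness Study Design states: "In addition, the team will establish short-term benefits (achievable after six-months of services) along with the program implementation conditions necessary to achieve them".

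Methods and Measures describes the two arms: "Participants will be randomly assigned to one of the two variants of the Parents as Teacher home visitation model, traditional or hybrid". It adds: "Both formats and all interventions included in the study are the current models of care for our existing PAT/YMP services". On size: "We expect a total of 30 participants, 15 in each arm of the study".

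The only group outside these arms is observational. Methods and Measures says that analysts will use techniques such as propensity score matching "to create a matched control group". Under Study Timeline, a team member is to "securely extract health data for treatment and matched control group participants from the Epic system". Outcome Measures describes the Epic information as "including completion of Well-Child Visits and recommended immunizations".

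Under Proposed Statistical Analyses, the inferential paragraph plans tests of change from baseline to end of study for PHQ 9 and PFS. It also plans comparisons between the models for PFS, schooling, breastfeeding, contraception, StimQ2-I, well-child visits and immunizations. It names no test against the matched control. Separately, Outcome Measures makes fidelity-of-implementation (FOI) scores a predictor, with the aim of finding a minimum level of service.

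**The concern.** A statement that services produce certain benefits by six months needs a comparison with mothers who did not receive the services. The randomized comparison cannot supply it, because both arms are served. The matched control could supply it at most for outcomes held in Epic.

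That leaves change over time and FOI associations. Mothers enter immediately after delivery, so mood and family functioning may change without any program. The first PFS is taken in service week one, so it is not a clean pre-service value. FOI scores are not assigned at random, and each model has its own checklist.

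If the plan is followed as written, natural change after birth could be reported as program benefit and carried into the cost-effectiveness conclusion, and into the claim that short-term results foreshadow later ones. Likewise, if the arms look alike, the data cannot separate two effective models from two ineffective ones.

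**Working it through.** The plan gives no alpha, power, effect size or standard deviation, so there is no figure of its own to reproduce. The check has three steps.

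**1. Comparator available for each outcome** (from Outcome Measures, Proposed Statistical Analyses and Study Timeline)

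| Outcome | Source | Outside comparator named? | Analysis named |
|---|---|---|---|
| Well-child visits, immunizations | Epic | Matched control | Between models |
| PHQ 9 | Study, baseline and end | No | Change |
| PFS | Study, week one, week six, end | No | Change; between models |
| StimQ2-I | Study, end only | No | Between models |
| ASQ 3, ASQ:SE 2 | Study, 2, 4 and 6 months | No | None named beyond descriptive |
| Schooling, breastfeeding, contraception | Study monthly questionnaire | No | Between models |
| Infant milestones | Study monthly questionnaire | No | None named beyond descriptive |

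Two outcomes have a named outside comparator and nine do not (PHQ 9, PFS, StimQ2-I, two ASQ instruments, three maternal items, milestones). For StimQ2-I the plan says: "The StimQ2-I will be implemented at the end of study".

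**2. What a significant change would show if services had no effect**

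Assumptions, not in the documents: two-sided alpha 0.05, paired t-test, normal change scores, and a natural drift of m standard deviations of the change score. The probability of significance comes from the noncentral t distribution with n − 1 degrees of freedom and noncentrality m√n. For m = 0.5 and n = 30, the noncentrality is 0.5 × √30 = 2.74 and the critical value is 2.045, giving 0.75.

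| Natural drift m | n = 30 (arms pooled) | n = 15 (one arm) |
|---|---|---|
| 0 | 0.05 | 0.05 |
| 0.2 | 0.19 | 0.11 |
| 0.3 | 0.36 | 0.19 |
| 0.5 | 0.75 | 0.44 |
| 0.8 | 0.99 | 0.82 |

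The documents do not give the size of the drift, so the whole range is shown. A significant change is compatible with a program effect of zero.

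**3. What the randomized contrast can show**

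With 15 mothers per arm, all analysed:

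- Standard error of a difference in means, in SD units: √(2/15) = 0.365.
- 95% half-width: t(28 df, 0.975) × 0.365 = 2.048 × 0.365 = 0.75 SD.
- For a binary outcome near 50%: 1.96 × √(2 × 0.25/15) = 0.36, or 36 percentage points.
- At the assumed alpha, 80% power needs a difference of about 1.06 SD (t-test). Power at 0.5 SD is about 0.26.

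Loss to follow-up would widen these intervals. Adjustment for a baseline value could narrow them for PHQ 9, but no correlation is given. Either way, a non-significant contrast leaves large differences between the models open.

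**The case against.** The strongest reply is that the Objectives compare two models, that a randomized two-arm comparison suits this, and that any trial of one active program against another leaves open whether both work. That stands: the design is not at fault for its main objective, and most tests in the inferential paragraph are already between models.

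A second reply is that the disputed sentence sits among plans to inventory costs and identify outliers, so the verb may mean only listing which benefits belong in a cost study. That reading is possible. But the sentence ties the benefits to a period of services and to the conditions needed to achieve them, which attributes them to the program.

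Third, a pilot of 30 is expected to be imprecise. True, and the small size is not the complaint here. Precision matters only to how a null contrast is read when costs are compared.

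Four stronger readings are tempting, but the documents do not support them:

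- **The Epic controls are an unserved group.** Nothing says so. Under Subject Recruitment Methods, mothers who decline the study remain eligible for services.
- **Epic can supply only two outcomes.** The list is introduced as inclusive. Two are named; others may exist.
- **Infant maturation will be reported as benefit.** No before-and-after test of infant outcomes is named. The lack of a StimQ2-I baseline does not harm its one planned use, a randomized comparison.
- **Hybrid will win because it is cheaper.** No hybrid cost and no decision rule are stated, and the virtual course also has a cost. Even the visit counts are unsettled. Six months from enrollment gives 2 × 6 = 12 traditional visits against about (26 − 6)/4.35 = 4.6, that is 4 to 5, hybrid visits. The Study Timeline also says both models should allow at least six months of home visiting, which would give hybrid at least 6. Those statements need reconciling.

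**Conclusion.** The concern holds, confined to the absolute-benefit statement. The randomized comparison supports estimates of how the two models differ. Changes in PHQ 9 and PFS and associations with FOI can be described but not credited to the program. Nine of the eleven named outcomes have no named outside comparator. The other two have a matched group with no specified analysis and unknown receipt of services.

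The risk of mistaking drift for benefit depends on an unknown drift: over 0.2 to 0.8 SD of the change score, the pooled paired test would be significant 19% to 99% of the time with no program effect. The 0.75 SD half-width assumes 15 analysed per arm and no covariate adjustment.

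A reader might infer that the trial as a whole cannot meet its objective. It can address it, subject to its precision; what should go is the claim that goes beyond the comparison.

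**What to change.** 1. In Proposed Cost Effectiveness Study Design, replace the undertaking to establish benefits with: *estimate the hybrid-minus-traditional difference in each six-month outcome, with 95% CI*.
2. In Proposed Statistical Analyses, add: *Within-arm changes in PHQ 9 and PFS, and associations with FOI scores, are descriptive. They will not be reported, or entered in the cost-effectiveness analysis, as program benefit.*
3. Add: *A non-significant difference between models will not be read as equal effectiveness when costs are compared.* Cite the expected half-width of about 0.75 SD at 15 per arm.
4. Specify any comparison with the matched controls. Limit it to outcomes available in Epic and label it non-randomized. Call it program versus no program only if the controls' receipt of Imprints Cares services is ascertained and served mothers are excluded.

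Items 1 to 3 are wording and need no new participants or data. Item 4 needs a check of the controls' service records only if the program-versus-no-program label is wanted. The real cost is that the sponsor gives up an absolute-benefit statement for most outcomes.

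### The family educator sets the monthly questionnaire dates with no common due date or window, so timing and completeness of breastfeeding, contraception and schooling data could differ by arm

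*Combined protocol and SAP*

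**What the plan says.** The Outcome Measures section introduces "a monthly questionnaire used to assess mother's status on continuance of secondary education, breastfeeding, and use of contraception". The Inferential Analyses paragraph then puts these outcomes into the between-arm comparison: "Tests also will be used to assess differences between the models on maternal outcomes such as continuance of secondary education, breastfeeding", with contraception named next. It gives no analysis time point and no missing-data rule for them.

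The milestone list under Study Timeline sets the timing: "Monthly questionnaires will be implemented with each participant, on a schedule developed by the family educator". Beyond that, the only limits are the word monthly and a timeline row running from project month 3 to project month 11, which is not tied to any mother's own enrollment date.

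Contact differs by arm. Under Methods and Measures, "Participants in the traditional PAT model will receive two home visits a month and participate in monthly peer (group) connections throughout the study period". For the hybrid arm, "After completion of the virtual program, young moms will begin receiving once a month home visits", together with monthly group sessions. The Study Timeline section adds that traditional home visits begin at enrollment, and hybrid home visits begin when the six-week virtual class ends.

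**The concern.** The plan gives its other questionnaires set times. The PFS is due at weeks one and six and at end of study, the ASQ 3 and ASQ:SE 2 at 2, 4 and 6 months, the PHQ 9 at baseline and end of study, and the StimQ2-I at end of study. Only the monthly questionnaire is left to the staff who deliver the service. The end-of-study battery does not list breastfeeding, contraception or schooling, so it offers no fixed-date backup for them.

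These three are status measures that can change within months, so the answer depends on when the question is asked. A monthly frequency limits the number of forms but does not align their dates between arms. If educators fit the form around their visits, the arm with more visits could be asked closer to the nominal month and could have fewer gaps. A difference between models would then mix the effect of the model with a difference in when, and from whom, data were obtained. Misaligned dates cannot be fully repaired after collection.

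**Working it through.** The plan states no figure on this point, so there is nothing to reproduce. The check counts scheduled home visits from the plan's own frequencies, then illustrates what a misalignment could do.

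1. **Inputs from the plan.** End of study is six months after enrollment, taken as 26 weeks, so one month is 26/6 = 4.33 weeks. Traditional: two home visits a month from enrollment. Hybrid: no home visits for six weeks, then one a month. There are 15 mothers per arm. Six monthly forms are expected per mother.

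2. **Home visits, traditional.** 2 × 6 = 12, enough to carry all six forms.

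3. **Home visits, hybrid.** The span after the class is 26 − 6 = 20 weeks, and 20/4.33 = 4.6 monthly intervals. With the first visit at week 6, visits fall at about weeks 6, 10.3, 14.7, 19.0 and 23.3. The next would be at week 27.7, after week 26. That is five visits.

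4. **Shortfall if forms follow home visits only.** 6 − 5 = 1 form, and 1/6 = 16.7%. The gap lies mainly in the virtual class: a month-1 form would be due at week 4.3, and the first home visit comes 6 − 4.33 = 1.7 weeks later.

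5. **Other hybrid contacts in the plan.** There is an initial meeting with the educator, the virtual class (number of sessions not given), the PFS in weeks one and six, the ASQ 3 and ASQ:SE 2 at 2, 4 and 6 months, and monthly groups after the class. Any of these could carry a form, so the true shortfall may be zero.

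6. **Timing illustration (assumed inputs, none from the plan).** Suppose 80% breastfeed at the start and a fraction s stop each month in both arms, so p(t) = 0.8 × (1 − s)^t. If one arm is asked w weeks earlier, the false difference is 0.8 × (1 − s)^(t − w/4.33) − 0.8 × (1 − s)^t. With s = 10% and w = 2, month 3 gives 61.2% − 58.3% = 2.9 points and month 6 gives 44.6% − 42.5% = 2.1 points. Over s = 5% to 20%, w = 1 to 4 weeks and t = 3 or 6, the range is 0.7 to 9.4 points.

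7. **Completeness illustration (assumed inputs).** The true rate is 50% in both arms, so 7.5 of 15 expected, and all missing mothers lack the outcome. One missing in one arm gives 7.5/14 = 53.6%. Three missing in the other gives 7.5/12 = 62.5%. The false difference is 8.9 points.

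8. **Scale of chance variation.** One mother is 1/15 = 6.7 points. At 50% in both arms the standard error of a difference is √(2 × 0.25/15) = 0.183, about 18 points. The 2.9-point example is 2.9/18.3 = 0.16 standard errors, and the top of the timing range is 9.4/18.3 = 0.51.

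**The case against.** The strongest reply is that the mechanism is assumed. The plan does not say that forms are completed at home visits, who administers them or by what route. It states one monthly rule for both arms, and the traditional arm's 12 visits still yield six monthly forms. Hybrid mothers are not out of reach during the class, since PFS data are collected from them in weeks one and six. All of this stands, and it is why the point is a risk only.

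A reader might go further in three ways that the documents do not support.

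- *That the hybrid arm loses up to a third of its forms.* This comes from rounding 4.6 down to four visits. Visits starting at week 6 give five. The Study Timeline section also aims for at least six months of home visits in both models; counted after the class, that would give the hybrid arm six visits and no shortfall in number, although end of study is set at six months from enrollment.
- *That the comparison is biased by several percentage points.* The rates of stopping, the offset and the pattern of missing data are all outside assumptions, and the resulting timing differences are small beside a standard error of about 18 points.
- *That the problem is lack of blinding.* The documents do not mention blinding. An educator delivering a model must know the arm, but the route described here is contact frequency, not knowledge of the arm.

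The questionnaire itself was still to be developed, and the Appendix refers to forms held with the IRB application. It may already ask for dates of stopping, so no omission is claimed there.

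What survives is that the plan states an actual rule, and that common due dates would be a better one. The small sample does not excuse it: a timing difference is systematic, and the plan treats short-term outcomes as pointers to longer-term results.

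**Conclusion.** The point holds as a cheap improvement. The plan lets the person delivering the arm-specific service set the dates of the only instrument it names for three outcomes compared between the models, with no anchor or window, while home contact differs by arm. Timing and completeness could differ by arm; the documents do not show that they will.

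The one size that follows from the plan's own frequencies is about one hybrid form in six (about 17%), mainly during the virtual class. It rests on forms following home visits only, on the first hybrid visit falling at week 6, and on follow-up of 26 weeks. The percentage-point figures are illustrations only and should not be quoted as an expected bias. The consequence is confined to interpreting the between-model comparisons of breastfeeding, contraception and schooling in a 30-person pilot.

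**What to change.** Replace the educator-set schedule with a common rule for both arms:

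- Forms are due at months 1 to 6 from enrollment, with one common window. ±7 days is a reasonable choice, though the exact width matters less than its being the same in both arms.
- When no contact falls in the window, the form is completed by phone or online link.
- The analysis uses status at the due date, not at the date of whichever visit carried the form.
- Completeness is reported by arm at each month.

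The cost is a short protocol change, less scheduling freedom for educators, and about one remote form per hybrid mother (month 1). It would be somewhat more if later visits, groups or ASQ contacts fall outside the windows. Sample size and services do not change. The fix aligns timing but does not blind the assessment. Having the research coordinator send the forms would not blind it either, because that role manages assignment.
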